7.1.2.3. Last Observation Carried Forward (LOCF)

For the WHO FC efficacy endpoint, if a subject is missing Week 24, their last observation will be carried forward to Week 24. If baseline is the last observation, it will be carried forward (BOCF).

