4.7. Visits

4.7.1. Windows

Each visit will be denoted by its visit “Week”. The first dose day is denoted as Day 1. In data listings, the relative study day of all dates from first dose will be presented.

Unless otherwise specified, scheduled assessments will be used for tabulated summaries. In the event of unscheduled visits, follow-up, or early treatment termination (ET) assessments, these will be reassigned to a scheduled visit for analysis purposes according to [Table 4](#) (RHC), [Table 5](#) (6MWT, WHO-FC, and NT-proBNP), [Table 6](#) (Clinical Laboratory Evaluations, Vital Signs, ECGs), and [Table 7](#) (Echocardiography and PAH-SYMPACT) for on treatment assessments. If multiple assessments occur within a single visit window, after reassignment of unscheduled visits and ET assessments, the assessment closest to the target day of the visit window will be used in the analysis. If there is a tie, the later assessment will be used in the analysis.

Table 4: Treatment Period Visit Windows: RHC

Target Scheduled Visit	Target Study Day ^a	Analysis Window Study Day ^a	
		Low	High
Baseline ^b	1	See Section 4.7.2	
Week 24	169	2	197 ^c

^a Study day will be calculated from first dose of study drug.

^b Baseline is defined in [Section 4.7.2](#).

^c Must be prior to first dose in the OLE.

Table 5: Treatment Period Visit Windows: 6MWT, WHO-FC, NT-proBNP

Target Scheduled Visit	Target Study Day ^a	Analysis Window Study Day ^a	
		Low	High
Baseline ^b	1	See Section 4.7.2	
Week 4	29	2	42
Week 12	85	43	126
Week 24	169	127	182 ^c

^a Study day will be calculated from first dose of study drug.

^b Baseline is defined in [Section 4.7.2](#).

^c Must be prior to first dose in the OLE.

Table 6: Treatment Period Visit Windows: Clinical Laboratory Evaluations, Vital Signs, and ECGs

Target Scheduled Visit	Target Study Day ^a	Analysis Window Study Day ^a	
		Low	High
Baseline ^b	1	See Section 4.7.2	
Week 4	29	2	42
Week 8	57	43	71
Week 12	85	72	105
Week 18	127	106	147
Week 24	169	148	182 ^c

^a Study day will be calculated from first dose of study drug.

^b Baseline is defined in [Section 4.7.2](#).

^c Must be prior to first dose in the OLE.

Table 7: Treatment Period Visit Windows: Echocardiography and PAH-SYMPACT

Target Scheduled Visit	Target Study Day ^a	Analysis Window Study Day ^a	
		Low	High
Baseline ^b	1	See Section 4.7.2	
Week 12	85	2	126
Week 24	169	127	182 ^c

^a Study day will be calculated from first dose of study drug.

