5. ANALYSIS POPULATIONS

Table 8 defines the analysis populations to be used.

Table 8: Analysis Sets

Analysis Sets	Description
Screened	All subjects who sign the informed consent form (ICF).
Safety	All subjects who receive any amount of study drug. Treatment assignment will be based on the treatment actually received.
Intent-to-Treat (ITT)	All subjects randomized into any one of treatment groups. Treatment assignment will be based on the randomized treatment.
Modified Intent-to-Treat (mITT)	All ITT population subjects with an evaluable baseline and at least 1 post baseline PVR assessment. Treatment assignment will be based on the randomized treatment.
Per Protocol (PP)	All mITT subjects who have completed treatment with $\geq 80\%$ treatment compliance (actual, see definition in Section 8.1) without any major protocol deviations,. Treatment assignment will be based on the treatment actually received.
Treatment Completer	All mITT subjects who complete 24 weeks of treatment with no dose reductions or dose interruptions. Treatment assignment will be based on the randomized treatment. Sensitivity analyses may be conducted based on the treatment actually received. No missing data will be imputed for these analyses. Any substantial differences between conclusions based on the ITT, mITT and the completers' populations will be investigated.

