7.1.2.1. Missing at Random (MAR): Multiple Imputation

For the primary analysis of PVR, 6MWT, and NT-proBNP efficacy endpoints, subjects who miss an assessment for reasons other than death or other tolerability reasons, will be imputed using multiple imputation (MI) methodology based on the treatment group for time points at which no value is observed. An intercurrent event meeting will be held prior to database lock and unblinding with the medical monitor(s) and statistician(s) to review the missing efficacy assessments for each subject and determine if the missing data is MAR or missing not at random, (MNAR), i.e. informative missing.

MI will be performed under the assumption of MAR. Intermittent missing value(s) will also be replaced using MI. MI will impute 10 integer values using Markov Chain Monte Carlo (MCMC) methods assuming nonmonotone missing, a seed of 100201, 500 burn-in iterations, 100 iterations between imputations, and a non-informative prior. The imputation models based on treatment group will include randomization stratification factors, baseline WHO FC, baseline 6MWD, and baseline value of the endpoint and all previous values of the endpoint at each time point. Other baseline characteristics that may be explored will be documented in the CSR. It is anticipated that the imputation model will converge but should it not do so terms will be removed from the model to achieve convergence. The effects of any such model adjustment will be investigated.

Change from baseline to each post-baseline visit will be calculated based on observed and imputed data. Results from the analysis of each of the 10 imputed datasets will be combined using PROC MIANALYZE (Rubin's imputation rules, [Rubin 1987](#)).

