7.1.2.2. MNAR: Imputation for Deaths and Tolerability Reasons

For the primary analysis of PVR, 6MWT, and NT-proBNP efficacy endpoints, subjects who missed an assessment due to death, tolerability, or >10% change in parental prostainoid dose (including adding a new medication).will be imputed as the worst value in their planned treatment group at the specific visit.

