7.1.2.4. Other Assessments of Missing Data

To assess the impact of missing data and robustness of the results, the following sensitivity analyses will be performed for the primary and secondary endpoints:

- Observed case analyses
- Treatment Completers population analyses

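### WHO FC carries the last class forward to Week 24 with no exception for death, so a patient who dies is analysed in the last living class

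*SAP*

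**What the plan says.** SAP section 7.1.2.3 gives the whole missing-data rule for WHO FC: "if a subject is missing Week 24, their last observation will be carried forward to Week 24". If nothing was recorded after baseline, baseline is carried forward. The reason for the missing value plays no part.

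The other three primary and secondary endpoints are handled by reason. Section 7.1.2.1 limits multiple imputation to "subjects who miss an assessment for reasons other than death or other tolerability reasons". Section 7.1.2.2 covers the rest: "For the primary analysis of PVR, 6MWT, and NT-proBNP efficacy endpoints, subjects who missed an assessment due to death, tolerability" or because of a change in prostanoid dose "will be imputed as the worst value in their planned treatment group at the specific visit". Both sections name PVR, 6MWT and NT-proBNP. Neither names WHO FC.

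Section 7 makes ITT the primary population. Section 7.3.1 fits an ordinal logistic regression to the change in class, with categories from -II to +II and none for death. Section 7.1.2.4 states that "the following sensitivity analyses will be performed for the primary and secondary endpoints": observed cases and Treatment Completers. Section 5 defines the latter as "All mITT subjects who complete 24 weeks of treatment with no dose reductions or dose interruptions".

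**The concern.** Death is the worst possible course for functional class, yet the rule can score it as stability or improvement. A patient with no post-baseline assessment who dies counts as no change. One last seen improved counts as improved. Only one already recorded as worse counts as worse.

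The carried value can be old. "Table 5: Treatment Period Visit Windows: 6MWT, WHO-FC, NT-proBNP" lists Weeks 4, 12 and 24 only, and the schedule in Protocol section 1.3 has no WHO FC at Week 18 or at the follow-up/early-termination visit. Up to 12 weeks can pass between the last class and death, so decline may go unrecorded.

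At stake are the WHO FC odds ratio, one of three secondary results, and the Week 24 responder comparisons in section 7.3.1.1 (class I/II against III/IV, any improvement, any worsening). With unequal deaths, all of them can favour the arm with more deaths.

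**Working it through.** **Does another rule reach these patients?**

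- The intercurrent event meeting in 7.1.2.1 sorts missing values into MAR and MNAR, but the MNAR rule in 7.1.2.2 does not apply to WHO FC.
- Observed-case analysis drops a patient who dies without a Week 24 value.
- Treatment Completers requires 24 weeks of treatment, so deaths before then are out.
- SAP section 11 records the new WHO FC model but no death rule.

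One exception: a patient with a class recorded inside the Week 24 window (Days 127 to 182) who dies later is not missing and is unaffected.

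**How much could it matter?** The plan states no figure for WHO FC to reproduce; its only power figure concerns PVR.

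Inputs:

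- 30 per arm (SAP section 3).
- Deaths per arm: not given; 0 to 3 assumed.
- Change at Week 24 under LOCF, better/same/worse: active 8/19/3, placebo 4/22/4 (assumed).

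Model: proportional odds, logit P(outcome worse than category j) = a_j + b × active, OR = exp(b). OR below 1 favours active. Strata are omitted here.

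Under LOCF the table is the same however many of these patients died: OR 0.52 (95% CI 0.17 to 1.55), p = 0.24. Moving the deaths to a separate worst category gives:

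| Deaths | Last seen | OR with 1 / 2 / 3 deaths |
|---|---|---|
| Active only | unchanged | 0.61 / 0.72 / 0.83 |
| Active only | improved | 0.69 / 0.91 / 1.21 |
| Active only | already worse | 0.53 / 0.54 / 0.55 |
| Placebo only | unchanged | 0.47 / 0.42 / 0.38 |
| Placebo only | improved | 0.39 / 0.29 / 0.21 |
| Placebo only | already worse | 0.51 / 0.50 / 0.50 |
| Same number in each arm | unchanged | 0.55 / 0.58 / 0.61 |

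Three active deaths, one from each class, give 0.82.

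The p-values lie between 0.07 and 0.87, except for placebo deaths last seen improved (0.10 / 0.04 / 0.01). The two- and three-death versions of that row are extreme: they need 2 or 3 of only 4 improved placebo patients to die.

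If death is merged with the worse category instead, 1/2/3 active deaths give 0.60/0.69/0.79 (unchanged), 0.68/0.88/1.14 (improved) and 0.52 throughout (already worse).

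Responder rates with three active deaths last seen improved:

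- Improved: 8/30 becomes (8 − 3)/30 = 5/30, against placebo 4/30.
- Worsened: 3/30 becomes (3 + 3)/30 = 6/30, against placebo 4/30.

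**Checks.** Three pooled strata in the model (6/15/9 per arm, assumed; repeated random allocation) leave the median ORs within 0.01 of those above; the equal-deaths row, the one-from-each-class case and placebo deaths last seen improved were not rerun with strata.

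A second table has identical arms of 6/21/3, with 1, 3 or 5 deaths in one arm, all last seen unchanged. LOCF gives OR 1.00 in every case. Ranking death worst gives 1.14, 1.46 and 1.83 against the arm with deaths. Observed-case analysis gives 0.98, 0.95 and 0.92, so it does not correct the problem.

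**The case against.** The strongest reply concerns weight. WHO FC is one of three secondary endpoints, outside the Hochberg procedure of SAP section 7.1.6, and Protocol section 10.1 plans no formal hypotheses. Deaths are visible elsewhere: all-cause mortality, time to clinical worsening, time to clinical improvement (which requires absence of death) and fatal adverse events. The confidence interval of 0.17 to 1.55 is far wider than most of the shifts. All of this stands. It limits the consequence, but none of those outputs corrects the WHO FC odds ratio or responder rates.

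The size is hypothetical: deaths, class counts and last-seen classes are all assumed. Patients who die may well have been recorded as worse beforehand, and then almost nothing changes. This also stands, and the conclusion is conditional for that reason.

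Reporting class as last observed alive, with mortality shown separately, can be defended as a deliberate choice. The SAP does not present it as one, and for the three companion endpoints it chose otherwise.

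Finally, section 7.1.2.2 also covers tolerability and prostanoid changes, so the inconsistency is wider than death. That is true. A living patient with a missing class still has a functional class, however, which makes it a separate question.

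**Conclusion.** The point holds as a should-fix. The text is unambiguous: a patient who dies with Week 24 WHO FC missing is analysed in the last living class, and neither sensitivity analysis brings that death back.

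The bias favours whichever arm has more deaths and is not specific to the drug. Its size depends on the number of deaths and the last recorded class. On the assumed table, one to three active deaths move the odds ratio from 0.52 to as far as 1.21 if last seen improved, and to no more than 0.55 if already worse. In most scenarios the estimate changes but significance does not.

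With no deaths there is no effect. With equal deaths, the same last-seen classes and no difference among survivors, there is no between-arm bias.

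**What to change.** In SAP section 7.1.2.3, exempt deaths from LOCF and BOCF. Score a death before Week 24 in its own category, ranked worse than +II, and merge it with the worst observed category if the model is too sparse to fit. In the Week 24 comparisons of section 7.3.1.1, count deaths as worsened, as not improved, and in the class III/IV group. Record the rule in section 11. It is in keeping with section 7.1.2.2 but not dictated by it, since that section uses the arm's worst value. Handling of living patients with a missing class is left as it is.

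The cost is SAP wording and no new data. The downside is one more category in a sparse table; the merged fallback removes it and keeps most of the correction for deaths last seen unchanged or improved. The change should be made before unblinding. SAP version 2.0 is dated 28 June 2023 and the documents give no lock date. If treatment codes are already open, the analysis should be reported in the CSR and labelled post hoc.

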7.1.2.4. Other Assessments of Missing Data

To assess the impact of missing data and robustness of the results, the following sensitivity analyses will be performed for the primary and secondary endpoints:

- Observed case analyses
- Treatment Completers population analyses

7.1.3. Planned Analyses

7.1.3.1. Interim Analyses and Data Monitoring

No formal interim analyses are planned for the study.

7.1.3.2. Data Monitoring

An external, multidisciplinary, Independent Data Monitoring Committee (IDMC) will review the progress of the study and perform interim reviews of unblinded safety and efficacy data at regular intervals and provide recommendations to the Sponsor whether the nature, frequency, and severity of AEs and AESIs associated with IP warrant the early termination of the study in the best interests of the subjects, whether the study should continue as planned, or whether the study should continue with modifications. The IDMC may also provide recommendations as needed regarding study design. While the IDMC will be asked to advise the Sponsor regarding future conduct of the study, including possible early study termination, the Sponsor retains final decision-making authority on all aspects of the study. Please see IDMC Charter for further details.

The Clinical Endpoint Adjudication Committee (CEAC) including three Pulmonary Arterial Hypertension (PAH) expert physicians will adjudicate the clinical worsening events (CWEs) per Clinical Endpoint Adjudication Charter.

The RHC data will be adjudicated by the blinded medical monitors per the RHC Adjudication Process Document.

7.1.3.3. Final Main Study Analysis

Any data values requiring investigation or correction will be identified while programming the datasets and Tables, Figures, and Listings (TFLs). The database will not be locked until the identified issues are resolved.

The final main study statistical analysis will be conducted when the last subject has completed the main study and will be based on the locked database.

7.1.3.4. OLE Analyses

The study includes an open label extension (OLE) phase. Details of OLE analyses will be described in a separate OLE SAP and reported in a separate CSR.

7.1.4. Multicenter Studies

The randomization is not stratified by site. Likewise, analyses of efficacy data will not be stratified by study site. The number and percentage of subjects randomized by geographical region and study site will be summarized by treatment group and for all subjects.

7.1.5. Use of an “Efficacy Subset” of Subjects

Not Applicable.

7.1.6. Multiple Comparisons/Multiplicity

In order to control the Type 1 error rate for the primary efficacy endpoint, the comparisons between each active arm and the placebo arm will be tested using the Hochberg approach, where the two p-values (600 mg vs placebo and 300 mg vs placebo) will be ordered largest to smallest as $p(1) > p(2)$.

1. If $p(1) < 0.05$ then reject both null hypotheses.
2. If $p(1) > 0.05$, but $p(2) < 0.025$, then reject the null hypothesis associated with $p(2)$.

7.1.7. Examination of Subgroups

Subgroups will be defined based on baseline values, unless otherwise specified, and only if there are a sufficient number of subjects in each category of the subgroup, defined as ≥ 5 subjects per treatment group. The primary and secondary efficacy endpoints will be presented based on observed data (no imputation) for the following subgroups:

- Age Group (<65 years vs ≥ 65 years)
- Sex (Male vs Female)
- Race (White vs All Other Races; Asian vs Non-Asian)
- Geographic Region (North America vs Europe vs Rest of World)
- Duration of Disease (≤ 5 years vs > 5 years)
- Baseline PVR (≤ 700 dyn/sec/cm 5 vs > 700 dyn/sec/cm 5)
- Baseline WHO FC (II vs III)
- Baseline 6MWD (<450 meters vs ≥ 450 meters)
- Baseline NT-proBNP (≤ 300 pg/mL vs > 300 pg/mL)
- Baseline REVEAL Lite Score: <6 vs ≥ 6
- Baseline use of Selexipag (Yes vs No)
- Baseline use of Parenteral Prostacyclin (Yes vs No)
- Baseline use of Endothelin Receptor Antagonist (ERA; Yes vs No)

- Number of Background PAH Therapies. (<3 vs ≥ 3)
- Type of PAH: Idiopathic, Heritable, Drug and Toxin induced, Associated with CTD, Associated with Other (Congenital Systemic Pulmonary Shunt or HIV)

Additional subgroup analyses and/or revision of above subgroup definition may be specified after database lock to accommodate available data as appropriate.

7.2. Primary Efficacy Analysis

The primary efficacy analysis will test the following hypothesis:

- H_0 : The mean change from baseline in PVR at Week 24 is equal between placebo and rodatristat ethyl.
- H_1 : The mean change from baseline in PVR at Week 24 is different between placebo and rodatristat ethyl.

In cases of missing data occurring at Week 24, missing data handling rules are specified in [Section 7.1.2](#).

Percent change from baseline in PVR at Week 24 will be analyzed using an analysis of covariance (ANCOVA) model with terms of treatment, randomization strata and baseline PVR. Estimates of least-square (LS) means, standard errors (StdErr), and 95% CIs will be presented by treatment group. In addition, the LS mean difference comparisons between each active dose and placebo, the StdErr of the difference, and 95% CI of the difference will be presented.

In order to control the Type 1 error rate, the comparisons between each active arm and the placebo arm will be tested using the Hochberg approach, where the two p-values (600 mg vs placebo and 300 mg vs placebo) will be ordered largest to smallest as $p(1) > p(2)$.

1. If $p(1) < 0.05$ then reject both null hypotheses.
2. If $p(1) > 0.05$, but $p(2) < 0.025$, then reject the null hypothesis associated with $p(2)$.

Assumptions for the ANCOVA will be checked, and if not satisfied, parametric analyses will be corroborated with appropriate nonparametric analyses, such as the Wilcoxon rank sum test stratified by randomization strata. The Hodges-Lehmann estimation of location shift and confidence interval will be produced. If the model residuals are not normally distributed, ANCOVA analysis based on ranked data will be performed.

7.2.1. Additional Analyses of the Primary Endpoint

The rodatristat ethyl treatment groups will also be pooled and compared to placebo.

In addition to the primary endpoint, PVR values, change from baseline, and percent change from baseline to all visits will be analyzed in the same manner described above.

Summaries will be provided for the subgroups as specified in [Section 7.1.7](#) for the ITT Population. A forest plot of the LS differences and 95% CIs will be presented for Placebo versus Rodatristat ethyl 300 mg BID and Placebo versus Rodatristat ethyl 600 mg BID for the ITT and Treatment Completer populations.

7.3. Secondary Efficacy Analyses

7.3.1. Change from Baseline to Week 24 in WHO FC

The secondary efficacy analysis will test the following hypothesis:

- H_0 : The distribution of change from baseline in WHO FC at Week 24 is equal between placebo and rodatristat ethyl.
- H_1 : The distribution of change from baseline in WHO FC at Week 24 is different between placebo and rodatristat ethyl.

The analyses will compare placebo and rodatristat ethyl on the distribution of change from baseline in WHO FC at Week 24 using an ordinal logistic regression with treatment group and randomization strata as factors. The number and percentage of subjects in each category (-II, -I, no change, +I, +II) will be presented by treatment group.

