5. STUDY POPULATION

5.1. Inclusion Criteria

Patients are eligible to be included in the study only if all the following criteria are met:

- 1. Male and female patients must be at least 18 years of age at the time of signing the informed consent.
 - a. Male patients and female partners of childbearing potential must agree to use contraception as detailed in a Section 5.4.1 to the protocol starting at Screening, during the treatment period, and for at least 100 days after the last dose of IP. Male patients must refrain from donating sperm during this period.
 - b. Female patients of childbearing potential must agree to use contraception as detailed in Section 5.4.1 starting at Screening, during the treatment period, and for at least 4 weeks after the last dose of IP.
- 2. Body mass index (BMI) $\geq 18 \text{ kg/m}^2 \text{ and } \leq 40 \text{ kg/m}^2$
- 3. Patients with symptomatic PAH belonging to one of the following 2018 Clinical Group 1 sub-types:
 - a. Idiopathic PAH
 - b. Heritable PAH
 - c. Drug- or toxin-induced
 - d. PAH associated with:
 - 1. Connective tissue disease
 - 2. Congenital systemic to pulmonary shunt (atrial septal defect, ventricular septal defect, patent ductus arteriosus) repaired at least one year prior to Screening
 - 3. Human immunodeficiency virus (HIV) infection if diagnosed with HIV, must have stable disease status defined as follows:
 - a. stable treatment with HIV medications for at least 8 weeks prior to Screening
 - b. no active opportunistic infection during the Screening Period
 - c. no hospitalizations due to HIV for at least 4 weeks prior to Screening
- 4. WHO FC II or III
- 5. Confirmed diagnosis of PAH and meet all the following hemodynamic criteria by means of a screening RHC completed prior to randomization:
 - a. mPAP of >20 mmHg
 - b. $PVR \ge 350 \text{ dyne-sec/cm}^5$
 - c. Pulmonary capillary wedge pressure (PCWP) or left ventricular end diastolic pressure (LVEDP) of ≤ 12 mmHg if PVR ≥ 350 and < 500 dyne•sec/cm⁵, or PCWP/LVEDP ≤ 15 mmHg if PVR ≥ 500 dyne•sec/cm⁵
- 6. 6MWD of 100 to 550 meters at Screening

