10.4.1. Efficacy Analyses

Endpoint	Statistical Analysis Methods
Primary	Primary efficacy analyses will be performed using the m-ITT and PP populations. Percent change from baseline in PVR will be analyzed using an analysis of covariance (ANCOVA) with Baseline PVR as the covariate. Additional baseline characteristics may also be evaluated as covariates in the model. The estimated between-treatment differences, 95% confidence intervals (CIs), and p-values will be presented. For patients who discontinue from the study early, the last-observation-carried-forward method will be used to impute the PVR at Week 24.
Secondary	Secondary efficacy analyses will be performed using the m-ITT and PP populations: Change in cardiac index, mPAP, mRAP, SvO2 at rest, and PAC from baseline to Week 24 TTCW Change in WHO FC Change in 6MWD from baseline Change in right atrial size & RV function: TAPSE, tricuspid annular systolic velocity, and RV fractional area change from baseline REVEAL Lite 2 score Change in PAH-SYMPACT from Baseline to Week 24 Change in 5-HIAA (plasma and spot urine concentration) The change from baseline to Week 24 endpoints will be analyzed using an ANCOVA model with treatment as a fixed effect, randomization stratum and baseline assessment as covariates. The estimated between-treatment differences, 95% CIs, and p-values will be presented. The change in 6MWD from baseline to Week 24 will also be compared between groups using non-parametric analysis of covariance within the framework of the extended Cochran-Mantel-Haenszel test. For endpoints measured over time, a mixed effect of repeated measure model may be used as sensitivity analyses. Details of statistical methods will be provided in the SAP. The time from the first dose of IP until to the first clinical worsening event will be summarized using Kaplan-Meier estimates and compared between treatment groups using the log-rank test.

Endpoint	Statistical Analysis Methods	
Exploratory	Will be described in the SAP finalized before database lock	

Protocol RVT-1201-2002

Effective: 19JAN2022

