2.2. Double-Blind Phase Study Design

This study will compare the efficacy, safety, and tolerability of 2 dosing regimens of rodatristat ethyl to placebo in subjects with PAH over a 24 week treatment period. Investigational product (IP) will be administered on the background of stable PAH therapy.

Approximately ninety (90) evaluable subjects will be enrolled. Subjects will be randomized 1:1:1 to placebo, 300 mg BID, or 600 mg BID of rodatristat ethyl.

Eligible subjects will be stratified based on the number of background PAH therapies they are receiving (1 vs 2 vs 3) and selexipag use (Yes/No). The number of subjects who are on a prostanoid infusion will be capped at 50% of the total enrolled. The number of subjects who are receiving selexipag will be capped at 20% of the total enrolled.

The study will consist of a Screening Period (up to 28 days in duration), a Baseline Period (Day 1), a 24-week Treatment Period (Main Study), and for subjects that early terminate or do not enroll an Open Label Extension (OLE), and a 4 week Follow Up Period (approximately 4 weeks after the last dose), for a total study duration of 32 weeks.

Subjects who complete the Main Study will have the option to enroll into an OLE and continue to receive rodatristat ethyl (those randomized to placebo will be re-randomized 1:1 to receive rodatristat ethyl 300 mg BID or 600 mg BID) for 6.5 years, until the Investigator or subject chooses to stop the IP, any stopping criteria in the Main Study are met, IP becomes commercially available, or the Sponsor stops the study for lack of efficacy or a safety signal (whichever preceding criteria comes first). In no case will a subject be allowed to exceed 10 years of exposure unless the product is approved for a chronic indication.

All participating subjects will be required to be on a stable background therapy for PAH with mono, dual or triple combination therapy (which may include currently approved prostanoid therapies) at the time of Screening. All subjects will maintain their standard of care (SOC) regimen at entry for the duration of the study. Refer to Section 6.6.2 for more details.

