7.1. Statistical/Analytical Issues

7.1.1. Adjustments for Covariates

For comparison of treatment groups with respect to change and percent change from baseline, analysis of covariance (ANCOVA) and restricted maximum likelihood (REML) based mixed model repeated measures (MMRM) models will be used. The corresponding baseline value will be used as a covariate in the model.

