11. CHANGES TO PROTOCOL PLANNED ANALYSES

- The exploratory objective “To evaluate the effect of rodatristat ethyl on the plasma concentration of selexipag and ACT333679” was reclassified as a PK/PD objective given it is assessing the drug concentrations.
- The Enrolled analysis set was relabeled to the “Screened” analysis set for clarity.
- The Safety analysis set was modified to include all subjects who received IP, regardless of randomization or not, to align with ICH E9 principles.
- The mITT analysis set was updated to specify at least one post-baseline PVR assessment (primary endpoint), instead of general efficacy assessment.
- The PP analysis set was updated to specify “who have completed treatment with $\geq 80\%$ treatment compliance” instead of general “complete Week 24”.

- The Treatment Completer analysis set was added.
- For primary endpoint analysis, missing data imputation was updated from LOCF to using multiple imputation for data MAR and worst observation for data NMAR.
- Analysis of WHO FC was updated from an ANCOVA model to ordinal logistic regression as it is a categorical endpoint.
- Analysis of 6MWT was updated from non parametric analysis of covariance within the framework of the extended Cochran Mantel-Haenszel test to aligned rank stratified Wilcoxon test with Hodges-Lehman estimates for consistency with drugs with similar indications.
- Physical examinations will be listed only.
- An additional definition of the TTCW endpoint was added.
- Additional exploratory endpoints added to specify all visits will be analyzed for secondary, additional, and exploratory endpoints where appropriate.
- Additional safety analyses were added to further characterize the risk profile.

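### The WHO FC model omits the baseline covariate that the protocol planned, without declaring it, so the estimate is exposed to chance imbalance in entry class

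*SAP*

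**What the plan says.** Protocol 5.1 admits "WHO FC II or III" only. Protocol 10.4.1 lists change in WHO FC among the secondary endpoints and assigns the change endpoints an "ANCOVA model with treatment as a fixed effect, randomization stratum and baseline assessment as covariates".

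SAP 7.3.1 replaces this with a comparison "using an ordinal logistic regression with treatment group and randomization strata as factors". The accompanying table is specified as follows: "The number and percentage of subjects in each category (-II, -I, no change, +I, +II) will be presented by treatment group". SAP 7.3.1.1 repeats the analysis at Weeks 4 and 12. It adds three two-way comparisons (class I/II against III/IV, any improvement, any worsening), each by a CMH test on the randomization factors and by Fisher's exact test.

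The randomization factors (SAP 2.2) are number of background therapies and selexipag use. SAP 7.1.1 says "The corresponding baseline value will be used as a covariate in the model", but the sentence before it names only ANCOVA and MMRM. SAP Section 11 records the switch in these words: "Analysis of WHO FC was updated from an ANCOVA model to ordinal logistic regression as it is a categorical endpoint". It does not mention the baseline term. SAP 7.1.7 lists baseline class II against III as a subgroup for the primary and secondary endpoints, on observed data.

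**The concern.** WHO FC has four steps and patients start on one of two. A class II patient can improve by one step or worsen by two. A class III patient can improve by two or worsen by one. If the chance of improving or worsening differs by entry class, the expected change in an arm depends on its mix of classes. Nothing in the randomization balances that mix, and nothing in the 7.3.1 model corrects for it.

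The stated reason for leaving ANCOVA, that the endpoint is categorical, explains the change of model type but not the loss of the covariate. The SAP models for PVR (7.2) and NT-proBNP (7.3.3) both keep their baseline term. SAP Section 1 says that substantial differences from the protocol are identified in Section 11, and this one is not. At stake are the estimate for a secondary endpoint and some precision.

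**Working it through.** **1. The plan's own power figure.** The only one is for PVR: 30 per arm, difference 0.75 SD, two-sided 0.05. Normal approximation: 0.75 × √(30/2) = 2.905, and 2.905 − 1.960 = 0.945, giving 82.8%. The t test with 58 df gives 81.5%. Both agree with the stated 80% or more. No figure is given for WHO FC.

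**2. Which changes are possible.** Class II: −I, 0, +I, +II. Class III: −II, −I, 0, +I. Only class III can reach −II and only class II can reach +II.

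**3. How often entry class is imbalanced.** The class III share is not in the documents; 30-70% is assumed. With two independent Binomial(30, p) counts, the SD of the difference is √(2 × 30 × p(1 − p)), which is 3.9 patients at p = 0.5 and 3.5 at p = 0.3 or 0.7. The exact probability of a difference of at least 6 is 15.5% at p = 0.5 and 12.0% at p = 0.3 or 0.7. For a difference of at least 3 it is 48-52%.

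**4. Shift in the odds ratio with no drug effect.** All transition rates are assumed. Improve/worsen percentages by entry class:

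| Pattern | Class II | Class III |
|---|---|---|
| P | 5/10 | 22/5 |
| A | 8/8 | 26/5 |
| B | 5/15 | 36/4 |
| C (no dependence) | 15/10 | 15/10 |

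Pattern P worked through, 18 against 12 class III:
- Improve: (18 × 0.22 + 12 × 0.05)/30 = 15.2% against (12 × 0.22 + 18 × 0.05)/30 = 11.8%. Odds ratio (0.152/0.848)/(0.118/0.882) = 1.34.
- Worsen: (18 × 0.05 + 12 × 0.10)/30 = 7.0% against (12 × 0.05 + 18 × 0.10)/30 = 8.0%. Odds ratio for not worsening (0.93/0.07)/(0.92/0.08) = 1.16.
- The proportional-odds model combines the two into about 1.27.

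Results at 18 against 12 (A to C simulated, 600 runs per case, likelihood-ratio test, no strata terms and no missing data):

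| Pattern | Odds ratio, unadjusted | Odds ratio, adjusted | Rejection, unadjusted / adjusted |
|---|---|---|---|
| P | 1.25-1.27 | 0.99 | 7-8% / 5-7% |
| A | 1.32 | 1.05 | 6% / 5% |
| B | 1.45 | 1.03 | 9% / 6% |
| C | 1.00 | 1.00 | 6% / 6% |

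Fitting the model to the expected proportions, which removes simulation noise, gives 1.27 (P), 1.24 (A) and 1.41 (B). At a smaller split of 16 against 14, pattern P gives 1.08.

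**5. Averaged over all randomizations, no drug effect.** The unadjusted odds ratio is 1.00. Rejection is 6-7% unadjusted and 5-7% adjusted, with a Monte Carlo SE of about 1 point.

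**6. Power at a true odds ratio of 3, unadjusted against adjusted.** P: 39% and 41% in one run, 42% and 44% in another. A: 45% and 48%. B: 41% and 51%. C: 47% and 47%. The Monte Carlo SE is about 2 points on each figure.

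**7. The class I/II against III/IV comparison in 7.3.1.1.** A class III patient counts as I/II only by improving; a class II patient does so by not worsening. Under pattern P the arm with 18 class III patients has (18 × 0.22 + 12 × 0.90)/30 = 49% in I/II. The arm with 12 has (12 × 0.22 + 18 × 0.90)/30 = 63%. With no drug effect the odds ratio is (0.628/0.372)/(0.492/0.508) = 1.74 in favour of the arm with fewer class III patients. The same imbalance therefore moves this comparison and the 7.3.1 model in opposite directions.

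**The case against.** SAP 7.1.1 opens with treatment comparisons on change from baseline and calls for the baseline value as a covariate, so the omission may be a drafting gap. That is possible. But the rule is tied to ANCOVA and MMRM, and 7.3.1 gives its own list of factors, so the two sections at least need reconciling.

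An imbalance would not be hidden. SAP 6.2 summarises baseline class by arm, and 7.1.7 already plans results by class II and III where each treatment group has at least 5 subjects. This stands, and it largely covers the case for a by-class table. It does not adjust the main comparison. The imputation model in 7.1.2.1 uses baseline class, but for PVR, 6MWT and NT-proBNP; WHO FC uses LOCF.

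The shift is also small against the noise. In pattern P, ln 1.27 = 0.24 and the SD of the log odds ratio is about 0.67, so the shift is about a third of a standard error. WHO FC is not powered and lies outside the Hochberg procedure, which covers only PVR. All of this stands and limits the weight of the point.

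Finally, one proportional-odds term for entry class does not fit perfectly. Under pattern P its odds ratio is (0.22/0.78)/(0.05/0.95) = 5.4 for improvement and (0.95/0.05)/(0.90/0.10) = 2.1 for not worsening. That is a reason to check the assumption, not to leave the term out.

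A reader might infer that the plan turns chance imbalance into false positive findings, or that substantial power is lost. Neither is supported. Rejection averaged over randomizations is about the same with and without the term, and the power gain vanishes if change does not depend on entry class.

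**Conclusion.** The omission is certain from the text: the protocol planned a baseline covariate, 7.3.1 has none, and Section 11 is silent. Its consequence is conditional. It needs an imbalance in the realised trial and a dependence of change on entry class. Given both, an 18 against 12 split shifts the odds ratio to about 1.25-1.45 with no drug effect, against about 1.0 adjusted, and an imbalance at least that large has probability about 12-16%. The power gain from adjusting is about 0 to 10 points. These sizes rest on assumed transition rates and an assumed class III share of 30-70%, and on simulations without strata terms or missing data. The point should be fixed because the remedy is cheap and restores what the protocol planned. It does not put the trial's main conclusions in doubt. The documents do not show whether the covariate was removed on purpose.

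**What to change.** - SAP 7.3.1, and its repeats at Weeks 4 and 12 in 7.3.1.1: add baseline WHO FC (II against III) as a factor in the ordinal logistic regression.
- SAP 7.3.1.1: add baseline class as a stratification factor in the CMH comparisons, above all for class I/II against III/IV. Six randomization strata × 2 classes gives 12 cells for 60 patients, about 5 per cell. With the pooling in Table 9 it is 3 × 2 = 6 cells, about 10 per cell, so state the pooling rule. Label Fisher's test as unadjusted.
- Check the proportional-odds assumption and say what replaces the model if it fails, given that −II and +II are each open to only one entry class.
- SAP 7.1.1: say whether the baseline rule extends to the ordinal model.
- SAP Section 11: record the change. If baseline is left out on purpose, declare and justify that there.

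Baseline class is already collected, so the cost is one degree of freedom in the model, sparser CMH strata and a few lines of SAP text. The by-class presentation needs little beyond what 7.1.7 already plans.
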